13.4. Definition of Analysis Visit Windows

Safety lab, vital sign, and ECG data will be assigned to analysis visit based on windowing (see table below). If more than one assessment (including the early termination or unscheduled assessments) falls within the same defined window, the assessment closest to the target day with non-missing data will be considered for analysis. If two assessment dates are at the same distance from the target day, the first assessment with non-missing data will be considered for analysis.

Study period	Analysis visit	Target day	Analysis window	Interval
Screening	Week -8 to -4	-28	-56 - < -21	NA
	Week -2	-14	-21 - ≤ -1	21
Main Period Controlled Portion	Day 1	1	1	1
	Week 2	14	2 - < 21	19
	Week 4	28	21 - < 42	21
	Week 8	56	42 - < 70	28
	Week 12	84	70 - < 91	21
Main Period Noncontrolled Portion	Week 14	98	91 - < 105	14
	Week 16	112	105 - < 126	21
	Week 20	140	126 - < 154	28
	Week 24	168	154 - < 189	35
	Week 30	210	189 - < 231	42
	Week 36	252	231 - < 273	42
	Week 42	294	273 - < 315	42
	Week 48	336	315 - < 350	35
Follow-up Period (for subjects not entering Part B)	Week 52	364	350 - < 371	21
	Week 54	378	371 - < 385	14
	Week 56	392	385 - < 406	21
	Week 60	420	406 - < 434	28

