#### 9. STUDY PROCEDURES

Table 1 outlines the timing of procedures and assessments to be performed throughout Part A of the study, once written informed consent has been obtained from the subject. Section 10.13 specifies laboratory assessment samples to be obtained. The schedule of visit dates should be established, either prior to or at the time of screening to allow subjects an opportunity to assess whether there are likely to be significant conflicts with other activities or planned absences. To the extent possible, subjects will be expected to adhere to the visit schedule, and any rescheduling of visits must be agreed, in advance, with the investigator and sponsor.

The investigator may, at his/her discretion, arrange for a subject to have an unscheduled assessment, especially in the case of AEs that require follow-up or are considered by the investigator to be possibly related to the use of study drug. The unscheduled visit page in the eCRF must be completed.

Study discontinuation procedures are described in Section 7.2.1.

Details regarding participation in Part B, the long-term extension, are provided in the appendices (Section 15).

Table 1: Schedule of Activities for Part A

Study Period	per	ening iod						Main period  Noncontrolled portion									Follow-up perio		s)
	8 we	eks) bjects A		Contr	olled p	ortion											All subjects not entering Part B		
Study Week	−8 to −4	-2	1	2	4	8	12	14 B	16	20	24	30	36	42	48	52	54	56	60 Exit
Study Day	–56 to –28	-14	1	14	28	56	84	98	112	140	168	210	252	294	336	364	378	392	420
Study Visit	1	2	3	4	5	6	7	8	9	10	11	12	13	14	15	16	17	18	19
Visit window (± days)	N/.	A C	0	3	3	7	7	7	7	7	7	7	7	7	7	7	3	3	7
Informed consent	X																		
Demographics	X																		
Medical history	X																		
Inclusion/exclusion D	X	X	X																
Vaccination E		X				X													
Concomitant medications	х	X	X	X	X	X	X	X	x	Х	Х	X	X	X	X	X	X	X	X
Physical examination F	X	X	X	X	X	X	X	X	X	X	X	X	X	X	X	X	X	X	X
12-lead ECG	X		X	X	X	x	x	X	X	x	x	X	X	X	X	x	X	X	X
Renal biopsy G	2	ζ.		X X															
Randomization			X																
Pegcetacoplan administration B				Group 1 only				All subjects											
Infusion site/pump safety assessment H				Group 1 only				All subjects											

Table 1: Schedule of Activities for Part A

Study Period	per (up	o to		Main period									(8	Follow-up period (8 weeks)					

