Urine pregnancy test		X	X	X	X	X	X	X	X	X	X	X	X	X	X	X	X	X	X
FSH, HIV, HCV, HBsAg, HBcAb R	х																		
AEs	Х	X	х	Х	Х	Х	X	X	Х	Х	Х	X	Х	X	X	X	X	X	X
Post-transplant immunosuppression plan documentation		x																	
Ophthalmologic evaluation (optional) S		XS													XS				

Abbreviations: ADA = antidrug antibodies; AE = adverse events;  $\beta$ -HCG =  $\beta$ -human chorionic gonadotropin; CDC = Centers for Disease Control and Prevention;

NOTE: When multiple assessments/procedures occur at the same time, order should be: vital signs, ECGs, blood collection/sampling, pegcetacoplan dosing.

CKD-EPI = Chronic Kidney Disease-Epidemiology Collaboration; ECG = electrocardiogram; eGFR = estimated glomerular filtration rate;

FSH = follicle-stimulating hormone; GFR = glomerular filtration rate; HBcAb = hepatitis B core antibody; HBsAg = hepatitis B surface antigen;

HCV = hepatitis C; N/A = not applicable; PK = pharmacokinetic(s); RBC = red blood cell; SC = subcutaneous;

SD-OCT = spectral domain optical coherence tomography.

A. Subjects who meet the medical history requirements will enter the screening period at Visit 1 and return for Visit 2, but all Visit 2 assessments need not occur in a single visit and Visit 2 can be split into multiple visits (eg, 2a, 2b).

- B. Subjects will self-administer SC pegcetacoplan after receiving appropriate training and sign-off by a research nurse or other personnel in their first treatment week. During site visits subjects will self-administer pegcetacoplan at the site, with the exception of the very first dose. Group 2 subjects will be trained on self-administration of pegcetacoplan and receive their supply of pegcetacoplan at the next scheduled clinic visit (Visit 7 or 8) following their biopsies.
- C. Visit 2 must occur at least 7 days after Visit 1 and at least 14 days prior to the Day 1 dosing date; the vaccinations and biopsy can occur any time after confirmation of eligibility based on Visit 1 data.
- D. Specific inclusion/exclusion criteria will be measured during screening, and some of them require confirmation prior to any activities of Day 1. See the inclusion/exclusion criteria in Section 7 for further detail.

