3.2. Randomization

Subjects will be randomized 3:1 to Group 1 (pegcetacoplan treatment throughout the Main Period) or Group 2 (no pegcetacoplan treatment for the first 12 weeks of the Main Period, followed by pegcetacoplan treatment), respectively.

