3.4. Sample Size

Given the exploratory nature of the study, no formal statistical hypothesis testing will be performed; therefore, the sample size is not based upon statistical power of the study. Up to 12 subjects will be enrolled into this study.

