13.2. Definition of Study Days

Unless otherwise noted, study days of an evaluation are defined as number of days relative to the Study Day 1 visit which is designated as Day 1, and the preceding day is Day -1, the day before that is Day -2, etc.

- For assessments on/after Study Day 1, study days are calculated as:
 - (date of assessment – date of Study Day 1 + 1)
- For assessments before Study Day 1, study days are calculated as:
 - (date of assessment – date of Study Day 1)

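### SAP 13.4's day windows leave out the last protocol-permitted day of Visits 7, 8 and 16, so a compliant Week 12 or Week 52 safety value can fall out of its by-visit summary

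*SAP*

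**What the plan says.** The scope is set in SAP 13.4: "Safety lab, vital sign, and ECG data will be assigned to analysis visit based on windowing". If several assessments share a window, "the assessment closest to the target day with non-missing data will be considered for analysis", and a tie in distance goes to the earlier one. Early-termination and unscheduled results compete on the same terms. Under SAP 13.2, "study days of an evaluation are defined as number of days relative to the Study Day 1 visit", so both groups are counted from Study Day 1.

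The SAP 13.4 windows that matter here are Week 12, 70 to <91 (Controlled); Week 14, 91 to <105, and Week 16, 105 to <126 (both Noncontrolled); Week 52, 350 to <371; and Week 54, 371 to <385. The last of these belongs to the block headed "Follow-up Period (for subjects not entering Part B)". The table has no Part B windows.

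The row "Visit window (± days)" in Protocol Table 1 gives 7 days either side for Visits 7, 8, 9 and 16, and 3 days for Visit 17.

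For Group 2, footnote B of Table 1 has subjects trained and "receive their supply of pegcetacoplan at the next scheduled clinic visit (Visit 7 or 8) following their biopsies". Protocol 9.2.3 likewise describes the first administration at Visit 7 or 8. Protocol 8.2 puts the start of Group 2 dosing no earlier than Week 13.

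**The concern.** A visit held on a day that the protocol allows should be reported as that visit. Here the upper bound of three windows is the very day on which the protocol tolerance ends, and the SAP excludes it. The value is relabelled as the following visit and then competes with the real one, usually losing.

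Week 12 ends the only randomized comparison of treated with untreated subjects, and SAP 3.5 assigns the Controlled Portion safety analyses to the Week 12 lock. Week 52 ends Part A treatment. With up to 3 controls, one missing value is a third of the control data in that row.

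There is a related gap for Group 2. The Controlled/Noncontrolled label follows calendar day alone, whereas these subjects change treatment state at their first infusion.

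**Working it through.** **Inputs.** Target days and tolerances come from Protocol Table 1, windows and the selection rule from SAP 13.4, and group sizes (up to 9 and up to 3) from SAP 3.

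**The SAP's own figures.** Upper bound minus lower bound gives 91 − 70 = 21 (Week 12), 105 − 91 = 14 (Week 14), 126 − 105 = 21 (Week 16), 371 − 350 = 21 (Week 52) and 385 − 371 = 14 (Week 54). These match the Interval column, as do all 16 rows after Day 1. Days 91, 105 and 371 are therefore excluded by design; the signs are not misprints.

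**Permitted days against windows.**

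| Visit | Permitted days | Days in own SAP window | Day lost | Where it goes |
|---|---|---|---|---|
| 7 (Week 12) | 84 ± 7 = 77–91 | 70–90 | 91 | Week 14, Noncontrolled |
| 8 (Week 14) | 98 ± 7 = 91–105 | 91–104 | 105 | Week 16, Noncontrolled |
| 16 (Week 52) | 364 ± 7 = 357–371 | 350–370 | 371 | Week 54, follow-up |

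Each loses 1 of 15 permitted days. The other 13 scheduled visits after Day 1 fit their windows.

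**Visit 7 on Day 91.** Visit 8 must then fall on one of Days 92–105, which gives 14 pairings. Week 12 has no scheduled value in any of them, because Visit 6 ends at Day 63. With Visit 8 on Days 92–104 (13 pairings), Visit 7 is 7 days from target 98 and Visit 8 at most 6, so the Visit 7 value leaves the by-visit summary. With Visit 8 on Day 105, Visit 7 stands as Week 14 and Visit 8 moves into the Week 16 window.

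**Visit 16 on Day 371.** It is 7 days from target 378. Visit 17, on Days 375–381, is at most 3 days away and wins in 7 of 7 pairings. A subject entering Part B has no Visit 17, and the Week 54 window does not apply to that subject, so no window covers the value.

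**Shared days.** Day 91 is permitted for Visits 7 and 8, Day 105 for Visits 8 and 9, and each is 7 days from both targets. Closing the bounds (Week 12 at 70–91, Week 14 at 92–105) rescues Visit 7 but takes Day 91 from Visit 8 and Day 105 from Visit 9. Day 371 is permitted for Visit 16 only, since Visit 17 starts at Day 375.

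**How often.** The documents give no distribution of visit days. I assume independent subject-visits with chance p of falling on the lost day, from 1% to 1/15 (visits spread evenly over the 15 days). The chance of at least one affected Week 12 value among n subjects is 1 − (1 − p)^n:

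- n = 12: 1 − 0.99^12 = 11%; 1 − (14/15)^12 = 56%; expected number at 1/15 is 12/15 = 0.8.
- n = 3 controls: 1 − 0.99^3 = 3%; 1 − (14/15)^3 = 19%.

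**Group 2 labels.** If the first infusion is at Visit 8, the pre-dose values taken then (Days 91–105) are labelled Noncontrolled although the subject is still untreated. If it is at Visit 7 on Day d within the Week 12 window, the pre-dose value is |d − 84| days from target. For d at or after 84, every later day is farther away and same-day ties go to the earlier assessment, so an available pre-dose value is always kept. Only with d before 84 can a later, post-dose value be nearer. With d = 80, for example, an unscheduled result on Days 81–87 would be chosen.

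**The case against.** The case against is substantial, and much of it stands.

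- **Nothing is deleted.** A reader might infer that safety values vanish. SAP 13.5 keeps every post-baseline assessment for determining potentially clinically significant values and lists them all. The loss is confined to by-visit observed and change-from-baseline summaries. The C3c biopsy endpoint and adverse events are not assigned by this table. The study is descriptive ("the sample size is not based upon statistical power of the study"), so no test is affected.
- **Two of the three days are ties.** Any set of non-overlapping day windows must give Days 91 and 105 to one visit, and the SAP consistently chooses the later. That is a convention, not an arithmetic slip. It is also why moving the bounds cannot repair Visit 7 without cost to Visit 8. Day 371 has no such excuse.
- **The frequency can be inflated.** Pooling three visits in 12 subjects gives 1 − (14/15)^36 = 92%. That counts Visit 8 moving to Week 16, which stays within the Noncontrolled Portion and touches neither Week 12 nor Week 52. The loss of a third of the control data concerns 3 subjects, so the relevant figure is 3% to 19%. Even spread overstates the risk if visits cluster near target.
- **Contamination of Week 12 by treated Group 2 values is not shown.** It needs an infusion before Day 84. Table 1 footnote B and Protocol 9.2.3 leave room for that, because Visit 7 may fall on Days 77–83. Protocol 8.2, with its Week 13 start, does not. This is a conflict within the protocol, not proof that the window fails.
- **The secondary endpoints are not shown to be affected.** Creatinine and eGFR are in the chemistry panel (Protocol Table 3), but SAP 6.2 names no visit mapping and does not invoke 13.4. Their exposure is an open question.

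**Conclusion.** The point holds as a narrow defect. Applied as written, SAP 13.4 mislabels protocol-compliant visits on one permitted day each for Visits 7, 8 and 16. Visits 7 and 16 are the ones that matter, because a value can leave the Week 12 or Week 52 summary altogether. Day 371 is lost needlessly; Days 91 and 105 cannot be resolved by day windows alone.

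The window comparison needs no assumption. The probabilities (11% to 56% among 12 subjects, 3% to 19% among 3 controls, at Week 12) rest on an assumed range of 1% to 1 in 15, independence, and full enrolment and attendance. They illustrate the size and are not a forecast.

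The Group 2 labelling is a secondary point. Untreated Visit 8 values labelled Noncontrolled follow directly from the rule when dosing starts at Visit 8. Treated values entering Week 12 remain conditional on a first infusion before Day 84.

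**What to change.** 1. In SAP 13.4, assign a scheduled visit made within its protocol tolerance to its nominal Table 1 visit. Use the day windows only for unscheduled and early-termination assessments, and state what happens to a scheduled visit made outside tolerance.
2. If day windows are kept for everything, at minimum set Week 52 to Days 350–371 and Week 54 to 372 to <385 (lengths 22 and 13). State that Week 52 applies to all subjects, including those entering Part B. This does not solve Days 91 and 105.
3. For these summaries, define Group 2's Controlled/Noncontrolled split by the actual first infusion, so that pre-dose values count as untreated and post-dose values cannot be selected for Week 12.
4. Reconcile Protocol 8.2 with Table 1 footnote B and Section 9.2.3 on when Group 2 dosing may start.
5. State in SAP 6.2 which visit mapping applies to eGFR and creatinine.

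The SAP items need wording and programming only, ideally before the Week 12 lock. Item 4 is a clarification of protocol text. No extra data are collected.

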13.5. Repeated or Unscheduled Assessments of Safety Parameters

For safety parameters, if a subject has repeated assessments before the start of investigational product, then the results from the final assessment made prior to the start of investigational product will be used as baseline. If end of study assessments are repeated or unscheduled, the last post-baseline assessment will be used as the end of study assessment for generating descriptive statistics. However, all post-baseline assessments will be used for Potentially Clinically Significant (PCS) value determination and all assessments will be presented in the data listings.

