- E. Vaccinations against N. meningitidis, S. pneumoniae, and H. influenzae are mandatory, unless documented evidence exists that subjects have received all recommended vaccines or are nonresponders to vaccination. Any required vaccines should be administered during screening (Day -14), and any required boosters should be administered at Visit 6 (Day 56), unless an alternative vaccination schedule has been agreed with the medical monitor, as described in Section 9.1.4. Subjects who withdraw from the study prior to a scheduled vaccine booster, as recommended by the current Advisory Committee on Immunization Practices adult immunization schedule, will be offered the opportunity to return to the site to receive the booster. Vaccination serum samples (for antibody titer) will be collected prior to subject receiving vaccinations on that study visit.
- F. Full physical examination will only be performed at Study Weeks -4, 1, and 52. Brief physical examinations will be conducted at all other clinic visits, as noted. A symptom-driven physical examination may be performed at other times, at the investigator's discretion. Body height (cm) will be measured during screening only and weight (kg) will be measured throughout study, during brief and full physical examinations. Edema should be assessed at every visit.
- G. Week 12 biopsy must occur at a time point between Weeks 12 and 14, inclusive; Group 2 subjects cannot begin pegcetacoplan administration until after the biopsy occurs. Week 52 biopsy must occur at a time point between Weeks 48 and 52, inclusive, but after completion of the 24-hour urine collection scheduled for Week 48.
- H. Between site visits, subjects will be instructed to report any infusion site reaction to the study staff. Pump use safety assessment will be performed by licensed health care professional (ie, investigator or nurse) within 30 minutes following study drug administration at all clinic visits and during at-home qualification. See Manual of Procedures for more details.

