3.1. General Description

This is an open-label, randomized, controlled, Phase 2 study, consisting of a single cohort of up to 12 subjects with clinical and pathologic evidence of recurrent C3G or IC-MPGN in a renal allograft. Subjects will be randomized 3:1 to Group 1 (pegcetacoplan treatment throughout the Main Period) or Group 2 (no pegcetacoplan treatment for the first 12 weeks of the Main Period, followed by pegcetacoplan treatment), respectively. The visit schedule will be the same, regardless of randomization.

Pathologic evidence of recurrence requires a biopsy-based diagnosis of C3G or IC-MPGN in the renal allograft, confirmed by a central pathologist. The diagnosis need not be the same in the native kidney and the renal allograft; for example, a subject with C3G in the native kidney and IC-MPGN post-transplant is still eligible for the study.

Subjects with either preexisting disease recurrence or upon initial identification of clinical and pathologic recurrence of disease will be invited to enter screening. Subjects must also have an eGFR of at least 15 mL/min/1.73m² and no more than 50% fibrosis on renal biopsy.

The study will require a total of 3 renal allograft biopsies, during screening, Week 12, and Week 52. Flexibility has been built-in for each biopsy as described below:

[figure not shown]
- Screening renal allograft biopsy: must occur within 4 weeks leading up to the day of randomization
 - A non-study biopsy may be used as the baseline biopsy provided it meets the following criteria:
 - it was performed no more than 12 weeks prior to Week 1
 - the subject has remained clinically stable since the biopsy with no changes in medication regimens that would be expected to significantly alter the baseline biopsy findings
 - the prior biopsy is available for central pathology review and includes all the required components of a study baseline biopsy.
- Week 12 renal allograft biopsy: must occur at a time point between Weeks 12 and 14, inclusive; Group 2 subjects cannot begin pegcetacoplan administration until after the biopsy occurs
- Week 52 renal allograft biopsy: must occur at a time point between Weeks 48 and 52, inclusive, but after completion of the 24-hour urine collection scheduled for Week 48.

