13.3. Definition of Baseline

For all evaluations unless otherwise noted, baseline is defined as the most recent non- missing measurement prior to the first administration of study drug (Study Day 1 for treatment group 1), or prior to/on the randomization date (Study Day 1 for treatment group 2). Baseline can be the same date as first dose, given the measurement is expected prior to first dose when only date information is available.

In by-visit summary tables, the baseline will be summarized using all available data, but also for each visit using only the baseline data from subjects with available data at the visit; hence the mean change from baseline will equal the mean visit value – mean baseline value.

Throughout this document ‘change from baseline’ refers to the actual change from baseline (i.e. visit value – baseline value).

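### SAP 13.5's baseline rule for repeated safety assessments has no Group 2 clause, so a retest before Group 2's delayed first dose can move that baseline past randomization, contrary to SAP 13.3

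*SAP*

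**What the plan says.** SAP 13.3 defines baseline "For all evaluations unless otherwise noted". Group 1 is anchored to its first dose. Group 2's baseline is the most recent non-missing value before first study drug "or prior to/on the randomization date (Study Day 1 for treatment group 2").

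SAP 13.5 covers repeated or unscheduled safety assessments. Its first sentence says that, where a subject has repeats before starting investigational product, "the results from the final assessment made prior to the start of investigational product will be used as baseline". No group is named. Its later sentences deal with end-of-study repeats and state that "all post-baseline assessments will be used for Potentially Clinically Significant (PCS) value determination".

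On timing, Protocol Table 1, footnote G, says "Group 2 subjects cannot begin pegcetacoplan administration until after the biopsy occurs". Footnote B has Group 2 trained and supplied with drug "at the next scheduled clinic visit (Visit 7 or 8) following their biopsies". On visits, SAP 3.1 says "The visit schedule will be the same, regardless of randomization". Protocol Table 1 accordingly schedules chemistry, hematology, vital signs and ECG for both groups on Day 1 and at Weeks 2, 4, 8 and 12.

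**The concern.** The start of investigational product and randomization fall on the same day for Group 1 but about 12 to 14 weeks apart for Group 2. A rule keyed only to the start of drug is harmless in the first group and gives a post-randomization baseline in the second. Because 13.3 gives way to anything noted elsewhere, a programmer could reasonably treat 13.5 as the specific rule for safety parameters.

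What is at stake is the Group 2 side of the safety tables. Group 2 is the only untreated comparator for laboratory tests, vital signs and ECGs, and only during the controlled portion. SAP 3.5 reports that portion by randomized group in the Week 12 Analysis. Two programmers, one following 13.3 and the other 13.5, could produce different Group 2 change-from-baseline and PCS tables from the same data. Creatinine is both a safety laboratory test (SAP 7.2) and a secondary efficacy variable (SAP 6.2), so a Group 2 subject could have two creatinine baselines in one report.

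**Working it through.** The plan gives no figure to reproduce. The check sets the two rules against the Group 2 calendar.

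**Inputs.** Up to 9 subjects in Group 1 and up to 3 in Group 2 (SAP 3). Nominal days from Protocol Table 1: randomization Day 1; Weeks 2, 4, 8 and 12 on Days 14, 28, 56 and 84; Visit 8 on Day 98. First dose: Day 1 in Group 1; Visit 7 (Day 84) or Visit 8 (Day 98) in Group 2.

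**Step 1: Group 1.** First dose is on Day 1, so the last value before drug is also the 13.3 baseline. The two rules agree.

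**Step 2: Group 2, repeated meaning a retest.** Take a laboratory value retested at Week 4. Under 13.3 the baseline stays on or before Day 1. Under 13.5 the retest is a repeat before the start of drug, so the rule applies. The final pre-drug assessment is then the retest itself or, taken literally, the pre-dose value at Day 84 or 98. Either one is after randomization. The documents give no retest frequency, so the number of values affected cannot be stated.

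**Step 3: Group 2, repeated including scheduled visits.**
- Shift in baseline: 84 − 1 = 83 days (Visit 7), or 98 − 1 = 97 days (Visit 8), nominal.
- Scheduled controlled-portion values after Day 1, per parameter: 4 visits × 3 subjects = 12 at most (Group 1: 4 × 9 = 36).
- Counted as post-baseline for PCS: all 12 under 13.3; 0 of these 12 pre-dose values under 13.5.
- Exception: a Group 2 subject first dosed at Visit 7 has a scheduled vital-sign reading 30 minutes after dosing (Protocol 9.2.3.3). It is post-baseline under either rule, and Day 84 lies in the Week 12 window (Days 70 to <91, SAP 13.4).
- Changes from baseline at Weeks 2 to 12 would still be calculated, because SAP 7.2 to 7.4 ask for them at each analysis visit. They would be measured from a later value, not lost.

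**Step 4: PCS criteria that use baseline directly.** SAP Table 2 has HR 2 + SBP 6 + DBP 4 + temperature 1 = 13 criteria, of which 4 are changes from baseline (SBP ±20 and DBP ±15 mm Hg). SAP Table 3 has HR 2 + PR 1 + QRS 1 + QTcF 3 + QTcF increase 2 = 9, of which 2 are changes (>30 and >60 msec). Together, 4 + 2 = 6 of 13 + 9 = 22. For these six, Group 2's later on-drug flags also depend on which baseline is used.

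**Step 5: the rest of the SAP.** Section 5.4 (medications) anchors Group 2 at Day 1, 7.1 (treatment-emergent events) anchors it at randomization, and 13.6.4 (missing severity) uses Study Day 1. All agree with 13.3. Section 4.3 also puts every subject randomized to Group 2 in the safety set, dosed or not; for one who leaves undosed, a baseline keyed to the start of drug has no reference date.

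**The case against.** The strongest reply is that repeated does not naturally mean every scheduled visit. Section 13.5 is headed for repeated or unscheduled assessments, and its second sentence, on end-of-study repeats, plainly concerns retests. The protocol uses the word in the same way for vital signs (10.3), laboratory follow-up (10.13) and rescreening (9.1.1). Section 13.3 names Group 2 and fixes its anchor, whereas 13.5 names no group and does not announce a departure. SAP 13.4 says "Safety lab, vital sign, and ECG data will be assigned to analysis visit based on windowing" and defines Weeks 2 to 12 without distinguishing the groups. Someone reading the whole SAP would probably apply 13.3.

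Most of this stands. A reader might infer from 13.5 that every Group 2 safety baseline moves by 83 to 97 days, that the Week 12 PCS table would have no Group 2 values from scheduled visits, or that Group 2 would have no changes from baseline in Weeks 1 to 12. The documents do not support these as settled consequences. The first needs the broad reading. The second fails for vital signs even on that reading, because of the 30-minute post-dose measurement. The third confuses a change measured from the wrong value with one that is missing.

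The reply does not dispose of the retest itself. A Group 2 retest after Day 1 and before first dose meets the wording of 13.5 on the narrow reading too. It is also fair that no hypothesis is tested, that individual values are listed so either calculation can be checked, and that the separate table shells, not seen here, may settle the matter. Those facts limit the consequence but leave the rule as it stands.

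**Conclusion.** The point holds as a drafting gap of limited size. On either reading, 13.5 gives Group 2 a post-randomization baseline whenever a safety parameter is retested after Day 1 and before first dose, and this conflicts with 13.3, 5.4 and 7.1. The larger effect (a shift to about Day 84 to 98 for all of Group 2, and 0 rather than 12 scheduled pre-dose values per parameter counted for PCS) depends on reading repeated to include scheduled visits. The wording does not exclude that reading, but the context makes it the less likely one.

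At most 3 of 12 subjects are affected, and only in the change-from-baseline and PCS tables for laboratory, vital-sign and ECG data. C3c staining and hence the primary endpoint, treatment-emergent adverse events, rejection, graft loss and observed values are unaffected. No direction of bias is claimed. The day counts assume nominal visit days and the subject-visit counts assume full Group 2 enrolment. The point is worth correcting before programming.

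**What to change.** Amend only the first sentence of SAP 13.5. Suggested wording: *For safety parameters assessed more than once up to the baseline cut-off, the last such assessment is the baseline, consistent with Section 13.3. The cut-off is the start of investigational product for Group 1 and the randomization date, inclusive, for Group 2.*

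Leave the end-of-study and PCS sentences as they are, so that they continue to apply to both groups. A broader statement confining the whole section to repeats on or before Day 1 in Group 2 should be avoided, because it would take Group 2 out of those two rules.

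The cost is one sentence in the SAP, with no new data and no change to any table already planned under 13.3. The table shells should be checked for the same anchor.
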